The aim of this present study is to evaluate the feasibility of integrating an at-home NST program into an existing healthcare system, to evaluate the interpretability of NSTs obtained at home within a high-risk obstetric population, to assess the number of abnormal and/or uninterpretable NST episodes incurred in a domiciliary setting, and define the subsequent patient care algorithm. Additionally, we will determine the patient and healthcare provider satisfaction and explore associated costs, benefits, and effectiveness for the healthcare system and patient.

With the results of this study, we plan to perform a larger study with a high-risk population residing remote from the healthcare center.

Purpose and Objectives

Mobile connectivity has the possibility to impact medical care of many patient populations, including pregnant patients. Non-stress tests (NST) for pregnant patients are currently conducted in clinical settings and are not routinely performed remotely. For rural and distant patients, this

Protocol Summary (ERICA) IRB_00077591
Page 3 of 17 IRB Approval 8/31/2018

means the need to travel for extended periods of time, multiple times per week, in order to receive these tests. Clinical facilities are also limited in the number of patients to whom they can provide clinical care by the physical space available for NSTs.

NST technology has been developed that enables remote NST monitoring. Preliminary data suggests that patients can reliably obtain a NST with self-application and have similar levels of satisfaction compared to patients receiving NSTs within a clinical setting.

We propose to test the Airstrip® Sense4BabyTM NST device in a local high-risk population in order to assess the feasibility of integrating an at-home NST monitoring program into an established health care system, as well as to evaluate patient and provider satisfaction associated with at-home monitoring.

Research questions

Primary Research Questions:

Can the Airstrip® Sense4BabyTM non-stress test device be integrated into an existing health care system in a manner that produces interpretable NSTs and allows timely interpretation and management by the healthcare provider?

If the device can be integrated, what steps are required and what are potential stumbling blocks for integration?

Secondary Research Questions:

- -How often do uninterpretable and/or abnormal NSTs occur?

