- -What is the care algorithm for these types of NSTs and how do these differ from patients receiving NSTs in clinic?
- -Are the patients and healthcare providers satisfied with the use of the NST device at home compared to receiving an NST in the specified clinic?
- -What is the cost-effectiveness of this approach for the health system and for patients?

Study Population

Age of Participants: Pregnant women ages 18 and older

Sample Size:

At Utah: 60 All Centers: 60

Inclusion Criteria:

Target population: The target population is high-risk pregnant women.

Accessible population: The accessible population is high-risk obstetric patients receiving care throughout the University of Utah Healthcare system and who receive their NSTs at MFDC.

- Singleton gestation
- Estimated gestational age of 32 0/7 -37 6/7 weeks
- Physician order for twice weekly NSTs
- Live within 60 mile radius of the University of Utah University Hospital or a hospital with an obstetric inpatient unit
- Reliable access to and connectivity with wireless Internet
- Reliable for communication and follow-up

Exclusion Criteria:

- Multifetal gestation
- Maternal age less than 18
- Plans to move prior to end of pregnancy
- No or limited access to internet and/or phone

Design

Observational Research Prospective Clinical Research

Study Procedures

Recruitment/Participant Identification Process:

Participants will be recruited by IRB approved research staff. Patients may be referred by their primary obstetrician, but we will not specifically ask providers to recruit patients.

Flyers and brochures will be placed in public areas throughout our recruitment catchment area including: University of Utah medical school, hospital and hospital clinics, campus boards, restrooms, etc.

We will screen patient appointment logs to determine women who may be eligible for this study. The inclusion/exclusion criteria will be reviewed with each patient's chart. Potentially eligible patients will be identified and invited to enroll upon presenting for a scheduled NST in the University of Utah Maternal Fetal Diagnostic Center.

Informed Consent:

Description of location(s) where consent will be obtained:

Consent will be obtained at clinics within the University of Utah covered entity. This may include: Madsen Clinic, Clinic 4 and the Maternal Fetal Diagnostics Center.

Description of the consent process(es), including the timing of consent:

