the result by a telephone call from the mid-level provider and appropriate follow-up arranged according to the NST management algorithm developed for this study. If the patient has trouble with using the device at home, the patient will be able to talk with the mid-level provider via telephone to troubleshoot issues.

The patient will also continue to receive an NST in clinic weekly, allowing each patient to serve as her own control in terms of NST interpretability, frequency of non-reactive NSTs, and satisfaction. Weekly on-site visits will also allow for educational opportunities and trouble-shooting. These NST schedules will be repeated on a weekly basis until delivery or until the provider discontinues the NST order.

Delivery and maternal / neonatal outcome information will be collected from the electronic medical record. Patients will be contacted after delivery to assess overall satisfaction with the NST at home versus in clinic.

Phase II

Upon completion of phase I enrollment (n=30), a second phase of enrollment will begin. Having demonstrated at-home NST interpretability and feasibility of integration into the healthcare system, the next step will be to use the remote NST testing to demonstrate feasible use in rural/remote settings. This will involve enrollment of up to 30 additional subjects. Inclusion/exclusion criteria, enrollment procedures, and study procedures will be identical to phase I recruitment, with the exception of the following:

- 1. Participants may receive NSTs up to twice weekly at home. During regularly scheduled obstetric visits (every 1 to 2 weeks depending on gestational age and circumstances), NSTs will be performed on site which will allow for educational opportunities and trouble-shooting. However, we will remove the requirement for once weekly on-site testing at the University of Utah Hospital.

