- 2. The requirement to be within a 60 mile radius of University Hospital will be removed. Instead, the requirement will be to be within a 60 mile radius of a hospital with an obstetric unit. Eligibility will be assessed upon enrollment and the nearest obstetrical hospital will be identified and recorded in the electronic medical record (NST nursing documentation and within the pink "sticky note" within the obstetrical episode). Clinical algorithms will be the same, except the referral hospital for urgent and emergent evaluations will be the closest hospital with an obstetrical unit. The interpreting NST nurse and physician will determine the recommended course of action and will communicate to the patient, per established protocols. The NST nurse and physician will also communicate to the responsible obstetric care provider at the nearest hospital for continuity of care.

Device Specifications and Logistics

NST transmission

NSTs obtained at home will be transmitted via technology included in the system in

conjunction with the patient's home wireless Internet system (Figure 1).

The Sense4BabyTM system measures the physiological parameters, then transmits wirelessly over Bluetooth the measured data to a proprietary application software running on a gateway device (Samsung phone), which then transmits it wirelessly (3G, 4G, or Wi-Fi) to a HIPAA-compliant, web database for storage. A provider, using any web browser on any capable computing platform, can then review the data via a custom web portal once the patient has ended the monitoring session and transmitted the data.

[figure not shown]

Figure 1: Diagram of information transmission

During the monitoring, the patient will be able to see the results of the monitoring, which can help guide the patient to troubleshoot problems they are having (Figure 2).

Figure 2: Picture of patient-viewable monitor

Figure 3: Image of gateway device with monitoring screen visible

NST data storage

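### No paired or clustered method is named for the own-control home-versus-clinic comparison, and Phase II permits remote women without requiring them or planning a result for them

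*Combined protocol and SAP*

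**What the plan says.** **Home versus clinic.** Under Study Design, Phase I, each woman has one home and one in-clinic NST per week until delivery or until the order ends. She acts as her own control for interpretability, non-reactive NSTs and satisfaction. Under Analysis, Analytic approach, the work is mostly descriptive. Chi-squared or Fisher's exact is named for nominal and binary outcomes. Student's t, Wilcoxon rank sum or Mann-Whitney U is named for continuous and ordinal ones, as needed.

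**Phase II.** Its purpose is that "the next step will be to use the remote NST testing to demonstrate feasible use in rural/remote settings". It keeps Phase I's rules: "Inclusion/exclusion criteria, enrollment procedures, and study procedures will be identical to phase I recruitment, with the exception of the following". There are two exceptions:
- Up to two home NSTs per week are allowed, and "we will remove the requirement for once weekly on-site testing at the University of Utah Hospital". On-site NSTs continue at regular obstetric visits.
- The radius around University Hospital is dropped. "Instead, the requirement will be to be within a 60 mile radius of a hospital with an obstetric unit". For each woman, "the nearest obstetrical hospital will be identified and recorded in the electronic medical record".

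The single inclusion list under Study Population joins both distance rules: "Live within 60 mile radius of the University of Utah University Hospital or a hospital with an obstetric inpatient unit". Under Recruitment, eligible women are "invited to enroll upon presenting for a scheduled NST in the University of Utah Maternal Fetal Diagnostic Center".

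The Sample size paragraph describes 10 and then 20 women. Zip code is a listed variable. Neither the Outcome list nor the Analysis section mentions phase, distance or remoteness.

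**The concern.** **(A)** An own-control design yields paired, repeated data. Chi-squared, Fisher's exact and rank sum/Mann-Whitney (one test under two names) treat every observation as coming from a different, unrelated person. Applied to pooled strips or paired scores, they ignore two things: the correlation among a woman's NSTs in one setting, and the correlation between her home and clinic results. The first makes the usual standard error too small and the second makes it too large. The affected comparisons are those the own-control design was meant to support.

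**(B)** Phase II carries the rural/remote aim, but a woman living beside University Hospital meets its criteria. The plan can be followed exactly with few or no remote women, and no planned result would separate them from the rest. This matters for what comes next, because the Significance section says that with these results "we plan to perform a larger study with a high-risk population residing remote from the healthcare center".

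**Working it through.** **Plan's own figures.** Phase I is 10 + 20 = 30 (Sample size calculations; Phase II section). Adding up to 30 in Phase II gives 60, the total under Study Population. This reproduces. No power, precision, alpha or margin is stated, so there is nothing further to reproduce. Every input below that is not one of these counts is an assumption.

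**(A) Standard error of the home-clinic difference**

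Let m be the NSTs per woman in each setting, r_w the correlation between two NSTs of one woman in the same setting, and r_c the correlation between her home and clinic NSTs. The true variance of the difference, relative to the variance an independent-sample test uses, is

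1 + (m − 1)·r_w − m·r_c

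Take m = 4 (four weeks, one NST per setting per week) and r_w = 0.3:

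| r_c | Variance ratio | Independent-sample SE / true SE |
|---|---|---|
| 0.3 | 1 + 0.9 − 1.2 = 0.70 | 1/√0.70 = 1.20 (20% too large) |
| 0.1 | 1 + 0.9 − 0.4 = 1.50 | 1/√1.50 = 0.82 (18% too small) |

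A simulation with 30 women gave variance ratios of 0.703 and 1.488.

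Two further simulations used 30 women and a two-sided 5% level:
- *Binary, 4 NSTs per setting, no true difference.* Chi-squared on pooled strips rejected between 1.0% of the time (women differ strongly overall, but not in their home-clinic contrast) and 9.3% (women differ mainly in that contrast). A within-woman test stayed at about 5%.
- *Continuous score, one pair per woman, correlation 0.5.* With no true difference, the independent t test rejected 0.6% of the time. With a true difference of 0.5 SD, its power was about 47%, against 75% for the paired t test.

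**(B) How many remote women Phase II might contain**

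Suppose a share f of enrolled women is remote and 30 are enrolled. The expected number is 30f, and the chance of none is (1 − f)^30.

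| f (assumed) | Expected remote women | Chance of none | Chance of at least 10 |
|---|---|---|---|
| 5% | 1.5 | 21% | <0.1% |
| 10% | 3 | 4% | <0.1% |
| 20% | 6 | 0.1% | 6% |
| 30% | 9 | <0.1% | 41% |
| 50% | 15 | <0.1% | 98% |

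Exact 95% intervals with one yes/no result per woman: 27/30 gives 73.5–97.9%, 9/10 gives 55.5–99.7%, and 4/5 gives 28.4–99.5%.

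Counting strips instead of women does not remove the problem. For k women with m NSTs each and within-woman correlation r, the effective number is k·m/[1 + (m − 1)·r]. With k = 6 and m = 8 (two home NSTs a week for four weeks, the most the schedule allows), 48 strips are worth:
- r = 0.1: 48/1.7 = 28.2
- r = 0.3: 48/3.1 = 15.5
- r = 0.5: 48/4.5 = 10.7

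**The case against.** **The tests are a generic menu.** A reader might infer that the plan commits own-control data to independent-sample tests. It does not. The Analysis section ties no test to the home-versus-clinic comparison, the choice is left open, and Student's t has a paired form. The primary outcome is a description, and no decision rule depends on a p-value. All of this stands. It does not close the gap for binary outcomes, which include interpretability and reactivity: both tests named there assume independence, and none of the named tests handles repeated NSTs.

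**Phase II was built for distant women.** A reader might infer that it shuts them out or is bound to miss them. The documents do not support that. They remove the weekly on-site requirement and the radius around University Hospital, and they use the nearest obstetric hospital for urgent referral. Staff could also seek out distant women, given the stated purpose. Permitting rather than requiring them is an ordinary pilot choice, and the Purpose section still speaks of a local population. What remains is that a rural/remote claim needs remote women in the data and a result for them.

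**The data exist.** Zip code and nearest hospital are recorded, so the investigators could show how many women were remote. That is fair: non-reporting is a possibility left open, not a planned omission.

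**The sizes are assumed.** This also stands. The standard-error effect changes sign with the chosen correlation, so no direction of bias is shown. The remote shares assume enrolment unrelated to distance, which Phase II's changes may alter.

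**The sample-size text omits Phase II.** This adds little, since 30 + 30 accounts for the 60.

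**Conclusion.** Both parts hold in limited form.

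(A) The design is within-woman and repeated, and the plan names no paired or clustered method. *If* the named independent-sample tests are used for home versus clinic, p-values can be too large or too small. In the illustrations the standard error was off by roughly a fifth in either direction, and the type I error ran from 1.0% to 9.3%. The correlations and the four-week duration are assumptions. Descriptive estimates are unaffected. This is mainly a Phase I matter, because Phase II drops the required weekly on-site test.

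(B) Phase II allows remote women but neither requires them nor plans a result by phase or remoteness. A rural/remote conclusion could therefore rest on few or none. How many there will be cannot be derived from the documents, and the shares shown are illustrations only. The results would still describe feasibility of testing with fewer on-site visits. What lacks support is extending them to rural or remote settings unless remote women are shown to be in the data.

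**What to change.** **(A)** For home versus clinic, state a within-woman analysis. Use either a paired t or signed-rank test on each woman's proportions or scores, or a GEE or mixed model clustered by woman. Base it mainly on Phase I, and stratify by phase if Phase II data are included. The cost is slightly more analysis work.

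**(B)** Without changing enrolment:
1. Before analysis, classify each Phase II woman as remote or not from the zip code already collected, for example by distance from University Hospital.
2. Report the number of remote women and their NSTs, and give obtainability, schedule-ability and interpretability for them separately. Use per-woman summaries with exact or small-sample intervals, or description alone if they are very few. GEE or clustered intervals would be unreliable with a handful of women.
3. Limit any rural/remote conclusion to these women, and describe the remaining Phase II results as feasibility of the reduced on-site schedule.

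This does not ensure that remote women are enrolled; it keeps the conclusion in line with who was. No new data are needed. The drawback is a possibly small subgroup with wide intervals.

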- 1. Turn on and unlock the gateway
- 2. Connect gateway to internet
- 3. Start the Sense4BabyTM application
- 4. Log-in
- 5. Navigate to the pairing screen
- 6. Insert the Toco in the dongle (this automatically turns the Central Unit on)
- 7. Successfully pair the PulseOx
- 8. Successfully pair the Central Unit
- 9. Uses adequate amount of transducing gel

10. Position the Central Unit on the abdomen, in a position suitable to hear the Fetal Heart

Rate

- 11. Attach the TOCO on the abdomen in a correct orientation
- 12. Secure the TOCO (with belt)
- 13. Secure the Central Unit (with belt)
- 14. Reset the TOCO to baseline
- 15. Collect FHR and TOCO data
- 16. Upload data to server

The patient's first NST will be obtained in clinic via the Sense4Baby™ system. After ensuring appropriate use and attainment of an interpretable, reactive, and reassuring NST, the patient will be discharged to home with the system.

NST appointment flow

At the time of the patient's appointment, the midlevel provider will call the patient to verify the appointment and ensure she is starting the NST. After this verification, the provider will communicate with the patient that he/she will call the patient in approximately 30 minutes to review the tracing and discuss results.

To initiate a monitoring/NST session, the patient will login into the Sense4Baby™ application on the gateway (via authenticated user name and password). She would then connect (pair) the application with the 2 Bluetooth sensors (Central Unit and pulse oximeter), which initiates a monitoring session.

The midlevel provider will utilize the portal to assess the interpretability of the NST strip. If the patient has trouble with the equipment or the midlevel provider identifies problems with the NST session, the patient and provider will troubleshoot accordingly. The individual identifying the issue will call the other. Troubleshooting the equipment will follow the manufacturers suggestions. Troubleshooting the NST strip will follow the created clinical algorithms. After a final disposition is decided, the encounter will be documented and closed.

NST billing

As a standard of care, NST sessions, whether in-home or in-clinic, will be billed according standard NST billing guidelines.

NST session moderating

The midlevel provider assigned to NSTs at the MFDC will log into the Sense4BabyTM portal

Protocol Summary (ERICA)

Page 11 of 17

IRB Approval 8/31/2018

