A data collection sheet will be developed and utilized in the study. A demographics intake sheet will be used when enrolling patients. Satisfaction questionnaires will be administered to study participants and involved providers. Patient satisfaction questionnaires will be conducted after the second in-home NST, at 2 weeks intervals after the initial survey if the patient is still pregnant, and at 6 weeks postpartum. Provider questionnaires will be conducted at the end of the study after all patients have been enrolled. An additional questionnaire will be administered to providers regarding the accessibility of the NST monitoring segments and interpretability – this will be conducted at the end of the study. Surveys will be built using REDCap. NST documentation within the electronic medical record (EPIC) will be according to the current NST workflow for on-site NSTs; details regarding management of uninterpretable or non-reactive NSTs will be extracted. Obstetric outcomes will be extracted from the patient's electronic medical record (EPIC).

Inclusion/exclusion criteria for which patients were screened out will be collected. Reasons

eligible patients declined study participation will also be collected.

Procedures performed for research purposes only:

Standard of care for this population includes 2 NSTs per week conducted in the out-patien clinic. Participants for this study will have 1 NST completed in clinic and will complete 1 NST at home, per week. Phase II participants may complete both NSTs at home if they n appropriate eligibility criteria. The only difference with home NSTs is that the NST devic patient-applied and the test is conducted at the patient's home. The test itself, and the interpretation, are not different than standard of care testing. Use of the device at home wi not change the patient's standard of care (twice weekly NSTs). The results of the home an clinic testing will be used to inform clinical care in the same way. Inadequate / uninterpretable tracings are a risk for both home and clinic NST monitoring and will requi further assessment per the described algorithms.

Related questionnaires, as described in study procedures section above, are for research purposes only.

Statistical Methods, Data Analysis and Interpretation

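### Does the qualifying clinic NST, which must be interpretable and reactive, tilt the home-versus-clinic comparison against home?

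*Combined protocol and SAP*

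**What the plan says.** Under Study Procedures, Patient education, the woman is taught the device in the diagnostic center. Her "first NST will be obtained in clinic" with the study system, and the device is released under this rule: "After ensuring appropriate use and attainment of an interpretable, reactive, and reassuring NST, the patient will be discharged to home with the system". The Phase I text describes release differently: the device is handed over once the woman has shown she can use it, and no tracing result is mentioned.

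Phase I then says that a weekly in-clinic NST goes on alongside the weekly home NST, "allowing each patient to serve as her own control in terms of NST interpretability, frequency of non-reactive NSTs, and satisfaction". The section on procedures done only for research gives the schedule: "Participants for this study will have 1 NST completed in clinic and will complete 1 NST at home, per week".

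The Outcome list names no home-versus-clinic contrast. The Analytic approach is mostly descriptive and has no rule on which NSTs enter the own-control comparison.

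**The concern.** Under the Patient education rule, every woman with a home NST has a clinic NST that passed on both outcomes being compared. No home NST carries such a guarantee. If that clinic NST is counted, the clinic failure rate is pushed down and home looks worse, although device and setting made no difference.

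There are reasons to think it might be counted. Women are "invited to enroll upon presenting for a scheduled NST in the University of Utah Maternal Fetal Diagnostic Center", so the qualifying NST could be that week's ordinary clinic test. The schedule has one clinic and one home NST per week. The research-only section lists no extra NST, only surveys: "Related questionnaires, as described in study procedures section above, are for research purposes only". Nothing in the plan marks the qualifying NST in the record.

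At stake is how the rates of uninterpretable and abnormal NSTs are read. These rates are a secondary research question, and the pilot is meant to lead to a larger study.

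**Working it through.** **The plan's own figure.** The sample size is 10 + 20 in Phase I and up to 30 in Phase II: 10 + 20 + 30 = 60, as stated. The plan gives no power, expected failure rate or number of NSTs per woman, so the failure rate p, the count k and the delivery week below are assumptions.

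**Size if only the passing NST is counted.** Let k be the clinic NSTs counted per woman, including the qualifying one, with the same true failure rate p at home and in clinic.

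- Clinic rate = p(k-1)/k; home rate = p; gap = p/k; ratio = k/(k-1), whatever p is.
- k = 2: 2.00; k = 4: 1.33; k = 7: 1.17.

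The entry criterion is "Estimated gestational age of 32 0/7 -37 6/7 weeks", a window of 5.857 weeks. Assume even entry, weekly clinic NSTs and k = floor(delivery week - entry week) + 1.

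- Delivery at 39 weeks: k is 7, 6, 5, 4 and 3 over the five full weeks and 2 over the last 0.857 week. Mean k = (25 + 0.857 × 2)/5.857 = 4.56. Pooled ratio = 4.56/3.56 = 1.28.
- Delivery at 38 weeks: every k is one lower. Mean k = 3.56; ratio = 3.56/2.56 = 1.39. A share of 0.857/5.857 = 15% of women would have no clinic NST after the qualifying one.

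**Example.** Take 30 women, 4 clinic and 4 home NSTs each, p = 10%. Home has 12/120 = 10%. Clinic with the qualifying NST has 9/120 = 7.5%; without it, 9/90 = 10%. The spurious gap is 2.5 points. With independent NSTs, the standard error of that difference is √(0.10 × 0.90/120 + 0.075 × 0.925/120) = 3.6 points.

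**Size under other handling.** Suppose the test is repeated until it passes and every attempt is counted. With equal risk across women, expected failures before the pass are p/(1-p) in 1/(1-p) attempts. The clinic rate is then [p/(1-p) + (k-1)p] / [1/(1-p) + (k-1)] = p, so the ratio is 1.00.

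If risk varies between women (beta distribution, p = 10%, within-woman correlation 0.1, so parameters 0.9 and 8.1), expected failures before the pass are 0.9/7.1 = 0.127. At k = 2 the clinic rate is 0.227/2.127 = 10.7% and the ratio is 0.94. At k = 4 it is 0.427/4.127 = 10.3%, ratio 0.97.

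| Handling of the qualifying NST | Home/clinic ratio, no true difference |
|---|---|
| Passing tracing counted, failures dropped | k/(k-1), pooled 1.28 to 1.39 |
| All attempts counted | 0.94 to 1.00 |
| Left out of the comparison | 1.00 |

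Simulation of 400,000 women per setting agrees. With the qualifying NST left out, the gap was at most 0.1 percentage point.

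**Which handling the text supports.** Phase I ties the control role to the clinic NSTs that continue each week in parallel with home testing. The qualifying NST precedes home testing, is done on the study device and sits under Patient education. Phase I also lists this teaching session apart from the weekly clinic NST. The schedule and billing text concerns how care is delivered, not which observations are compared. The natural reading leaves the qualifying NST out.

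**The case for a change.** The strongest case for a change is that the plan is silent, and silence lets the same data show home as worse, equal or slightly better. NSTs are documented under the usual on-site workflow, so someone extracting all clinic NSTs could pick up the qualifying one by default. If an unpaired chi-squared test were then run on 30 women with independent NSTs and p = 10%, the chance of falsely finding home worse (nominally 2.5%) would be about 17%, 10% and 8% at k = 2, 4 and 6. One sentence would prevent this.

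The mechanism stands, and so does the absence of a written rule. The rest is weaker:

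- The bias needs two choices that the plan nowhere makes: counting the passing tracing and discarding failed attempts (or the women who fail). The plan says that management details for uninterpretable and non-reactive NSTs will be extracted, so failed attempts would be on record.
- The first clinic NST can fail. The rule only holds the device back until a tracing passes.
- Phase II would show larger ratios. With on-site NSTs every two weeks, mean k is (4 + 3×2 + 2×2 + 0.857)/5.857 = 2.54 at 39 weeks, ratio 1.65. At 38 weeks it is (3×2 + 2×2 + 1.857)/5.857 = 2.02, ratio 1.98. But the own-control statement is made for Phase I only. For Phase II the plan says "During regularly scheduled obstetric visits (every 1 to 2 weeks depending on gestational age and circumstances), NSTs will be performed on site" and gives education and troubleshooting as their purpose.
- The home rates themselves do not depend on how the qualifying NST is classified.

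**Conclusion.** No change to the plan follows. This is a gap in the definition of an analysis set, and the plan followed as written does not produce the wrong result. An analyst who starts both series once the woman has the device at home, which is how Phase I describes the control, gets no bias.

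The apparent excess at home of 28% to 39% arises only if the passing tracing alone is counted. It also rests on assumed delivery at 39 or 38 weeks, even entry and weekly clinic testing. Under the other two treatments the ratio is 1.00, or between 0.94 and 1.00. The primary outcome is a description of feasibility and the analysis is mostly descriptive, so no planned decision depends on this contrast.

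The two descriptions of when the device is released (Phase I and Patient education) differ and should be reconciled. That is a separate drafting matter.
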